6.4 Exclusion criteria

1. Patients with known or apparent signs of other infectious causes of vaginal infection (BV, *Trichomonas vaginalis*, *Neisseria gonorrhoeae*, *Chlamydia trachomatis*, Herpes simplex, or human papillomavirus) at Screening.
2. Patients who are pregnant or breastfeeding.
3. Patients who were treated for VVC within 14 days prior to Screening.
4. Patients who are currently receiving anti-fungal therapy unrelated to VVC or has taken anti-fungal therapy within 14 days prior to Screening.
5. Patients who have received an investigational drug in a clinical investigation within 30 days prior to Screening.
6. Known/previous allergy or hypersensitivity to any product constituent or fluconazole.
7. Any medical condition that in the Investigator's judgements would make the patient unsuitable for inclusion.
8. More than 3 previous VVC infections during the last 12 months.

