6.5 Restrictions

During the study, the following medications are not allowed and should be avoided:

1. Anti-fungal medication related to VVC.
2. Other treatments for VVC (e.g. probiotics like Candicur and Multigyn).

Also see further information on rescue medication in [Section 7.5.2](#) and prior and concomitant medications in [Section 8.4](#).

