12.4.2 Primary endpoint analysis

In the estimand setting, the primary endpoint will, in addition to the definition stated in [Section 4.1.1](#), take the following identified intercurrent events into account:

1. Concomitant anti-fungal therapy or other treatments related to VVC due to lack of clinical performance prior to CVVS evaluation used for the primary endpoint definition.
2. Treatment discontinuation due to lack of clinical performance.
3. Rescue medication prior to the CVVS evaluation used for the primary endpoint definition.

Applying the composite strategy to account for these intercurrent events, these have been incorporated in the endpoint definition. Thus, to be defined as clinically cured on Day 7-14, the patient needs to have the last available CVVS score equal to or below 3 at Day 7-14, and that none of the above stated intercurrent events have occurred. If the CVVS score is above 3, or any of the intercurrent events has occurred, the patient is defined as not clinically cured on Day 7-14.

Patients with missing CVVS score at Day 7-14 and no intercurrent events will be considered as missing in the analysis.

The primary endpoint clinical cure rate on Day 7-14, as defined in the section will be calculated and presented together with a one-sided 95 % CI based on the Wilson score.

The primary performance objective of the trial is to show that the clinical cure rate is above 30 %, i.e. to show that the lower limit of the one-sided 95 % CI for the observed cure rate is above 30 %.

Hypotheses for the primary clinical performance endpoint

Null hypothesis: Clinical cure rate is less than or equal to 30 %.

Alternative hypothesis (one-sided): Clinical cure rate is above 30 %.

Sensitivity analyses to evaluate the effect of missing data for any of the 6 individual vulvovaginal signs and symptoms scores included in the CVVS score will be performed. Details on the sensitivity analyses will be described in the SAP.

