6.2.2 Restrictions

During the study, the following medications are not allowed and should be avoided:

1. Anti-fungal medication related to VVC – explicitly anatomical therapeutic chemical (ATC) codes J02A and D01AC.
2. Other treatments for VVC (e.g. probiotics like Candicur and Multigyn).

Since use of concomitant anti-fungal therapy or other treatments related to VVC due to lack of efficacy prior to CVVS evaluation used for the primary endpoint definition is considered an intercurrent event, a review of all concomitant medication will be performed prior to data base lock to classify the concomitant medication as an intercurrent event or not.

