7.9.2 Primary Variable

The primary endpoint is the clinical cure rate on Day 7-14, which is defined as the percentage of patients clinically cured at Day 7 to Day 14.

Clinical cure is defined as the absence of signs and symptoms of VVC in terms of having a CVVS score ≤ 3 .

Each of the following 6 vulvovaginal signs and symptoms will be individually scored using the scoring scale below.

- Vulvovaginal signs: erythema, oedema and excoriation
- Vulvovaginal symptoms: itching, burning and irritation

Scoring scale: each score should be objectively defined:

- 0 = none (absent)
- 1 = mild (slight)
- 2 = moderate (definitely present)

Study ID: CL4

3 = severe (marked, intense)

The CVVS score is the sum of the 6 individual scores. If any of the 6 individual signs and symptoms are missing, then the CVVS score will be considered missing. The last non-missing assessment of CVVS in the interval of Day 7-14 will be used. However, if the patient received rescue medication between the CVVS assessments at Day 7 and 14, CVVS data from Day 7 will be used. The same derivation will be made for secondary and exploratory endpoints made during the same time interval Day 7-14.

In the estimand setting, the primary endpoint will take the following identified intercurrent events into account:

1. Concomitant anti-fungal therapy or other treatments related to VVC due to lack of clinical performance prior to CVVS evaluation used for the primary endpoint definition.
2. Treatment discontinuation due to lack of clinical performance.
3. Rescue medication prior to the CVVS evaluation used for the primary endpoint definition.

Rescue medication prior to the CVVS evaluation used for the primary endpoint definition. From a practical perspective, bullet points 1 and 3 above will be regarded as the same in this study. Applying the composite strategy to account for these intercurrent events, these have been incorporated in the endpoint definition. Thus, to be defined as clinically cured on Day 7-14, the patient needs to have the last available CVVS score equal to or below 3 at Day 7-14, and that none of the above stated intercurrent events have occurred. If the CVVS score is above 3, or any of the intercurrent events has occurred, the patient is defined as not clinically cured on Day 7-14.

Patients with missing CVVS score at Day 7-14 and no intercurrent events will be considered as missing in the analysis.

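### An anti-fungal started for an unrelated reason before the primary CVVS is not clearly an intercurrent event, so a later score of 3 or less is counted as a device cure

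*SAP*

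**What the plan says.** Cure needs a last available CVVS of 3 or less in Day 7-14 and none of three intercurrent events (CIP 12.4.2, SAP 7.9.2):

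- Event 1: "Concomitant anti-fungal therapy or other treatments related to VVC due to lack of clinical performance prior to CVVS evaluation", where the evaluation meant is the one that decides cure. The CIP has the same condition: "Concomitant anti-fungal therapy or other treatments related to VVC due to lack of clinical performance".
- Event 2: stopping treatment for lack of performance.
- Event 3: "Rescue medication prior to the CVVS evaluation used for the primary endpoint definition".

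The SAP adds that, in practice, "bullet points 1 and 3 above will be regarded as the same in this study". It takes the last non-missing CVVS in the interval, but goes back to the Day 7 value if rescue was given between the two visits.

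Anti-fungals are described differently elsewhere:

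- At entry, CIP 6.4 excludes "Patients who are currently receiving anti-fungal therapy unrelated to VVC or has taken anti-fungal therapy within 14 days prior to Screening".
- On study, CIP 6.5 lists "Anti-fungal medication related to VVC", and CIP 8.4 words the restriction differently again.
- SAP 6.2.2 attaches two ATC groups to the restriction and says that "a review of all concomitant medication will be performed prior to data base lock to classify the concomitant medication". The aim is to decide which products count as intercurrent events. The criterion it gives for that review is again use for lack of efficacy.

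**The concern.** Events 1 and 2 depend on why something was done. Event 3 depends on the product being rescue, which CIP 7.5.2 and SAP 6.2.1 offer on Days 7 and 14 when VVC symptoms are at least as intense as on Day 0. A course of a systemic azole begun on Day 2 for a skin infection fits none of the three. Yet single-dose oral fluconazole is named in CIP 3.1 as a treatment for VVC and in CIP 7.5.2 as rescue. The plan therefore recognises that such a product can resolve the condition being scored, but has no explicit rule for it when the indication is something else.

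There is no control arm in which the same thing could happen. Any cure produced in this way goes straight into the one proportion that is compared with 30%.

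**Working it through.** **1. Follow one woman through the rule.** She starts a systemic azole on Day 2 for a skin infection, and her Day 7 CVVS is 3 or less.

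| Provision | Does it catch her? |
|---|---|
| Event 1 (SAP 7.9.2, CIP 12.4.2) | No, on the natural reading: not taken for lack of performance |
| Event 2 | No: she did not stop the pessary |
| Event 3 | No: not given as rescue |
| Review in SAP 6.2.2 | Only by discretion: its stated criterion is the same as event 1 |
| Per-protocol set (SAP 7.2.2) | Perhaps, if judged a deviation; that analysis is supportive, the FAS is main (SAP 7.9) |

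She is scored as cured in the main analysis.

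**2. Move the start to Day 9.** A woman with a CVVS above 3 on Day 7 attends on Day 14, because only women with both clinical and mycological cure, or who begin rescue on Day 7, skip that visit (CIP 5.4.5). If she takes an unrelated azole on Day 9, the return to the Day 7 value does not apply, since it is limited to rescue. A Day 14 CVVS of 3 or less turns a Day 7 failure into a cure.

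**3. Reproduce the plan's sample size.** Inputs from CIP 12.6 and SAP 5.1: null 30%, assumed 54%, one-sided 5%, power 80%.

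n = [(1.645 × √(0.30 × 0.70) + 0.842 × √(0.54 × 0.46)) / 0.24]² = 23.9, rounded up to 24. This agrees with the plan, which enrols 26.

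**4. Find the pass mark.** Wilson lower limit with z = 1.645 and p = x/n:

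L = [p + z²/(2n) − z√(p(1−p)/n + z²/(4n²))] / (1 + z²/n)

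For 12/26: (0.4615 + 0.0520 − 1.645 × 0.1028) / 1.1041 = 0.312.

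| Cures | Rate | Lower limit | Above 30%? |
|---|---|---|---|
| 10/24 | 41.7% | 26.8% | No |
| 11/24 | 45.8% | 30.4% | Yes |
| 11/26 | 42.3% | 27.8% | No |
| 12/26 | 46.2% | 31.2% | Yes |

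One woman moves the rate by 1/26 = 3.8 or 1/24 = 4.2 percentage points.

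**5. How often is the count exactly on the mark?** Binomial probability of exactly 12/26: 0.113 at a true 54%, 0.135 at the 41% seen in CL1. For exactly 11/24: 0.117 and 0.144.

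**6. Illustrate the effect on a false positive.** The documents give no frequency, so this is assumption only. Take a true device cure rate of 30%, a share f of women who take an unrelated anti-fungal before the CVVS used, and a probability c that such a woman scores 3 or less. CIP 3.1 quotes cure rates for standard treatment from as low as 35% at 7 days up to 87%; I run c from 35% to 100%. The observed rate is 0.30(1 − f) + cf, and success needs 12 or more of 26.

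| f | Chance of success, c = 35% | c = 64% | c = 100% |
|---|---|---|---|
| 0 | 0.060 | 0.060 | 0.060 |
| 1/26 | 0.063 | 0.081 | 0.107 |
| 2/26 | 0.066 | 0.105 | 0.172 |

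(The 0.060 at f = 0 is the exact error of the Wilson rule at n = 26, a separate matter.)

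**The case against.** **The wording can be read otherwise.** In event 1, both qualifiers may attach only to the other treatments, which would make any anti-fungal an event. Treating events 1 and 3 as the same could also be taken to drop the reason condition. CIP 8.4 can be read as discouraging anti-fungals generally, and SAP 6.2.2 ties its restriction to product codes. This stands as far as it goes: the azole user may be a deviation, and a reviewer might classify her as an event. But the criterion stated for the review points the other way, and two people applying the text could reach different answers.

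**Use is rare and the margin argument is general.** Criterion 4 leaves only anti-fungals newly begun in roughly one to two weeks. Any single classification is decisive when the count is on the pass mark, and that happens in about 11% to 14% of trials at the rates above. This stands, and it limits the size of the point.

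**Stronger readings that the documents do not support:**

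- *Every such woman is a false success.* CIP 3.1 reports short-term cure as low as 35% and some fluconazole resistance, and the pessary itself would cure some of them.
- *A woman who stops the pessary for local burning and uses a clotrimazole pessary is also scored as cured.* Clotrimazole pessary is a named rescue product and event 3 carries no reason condition, so she may already be caught.
- *Criterion 4 shows that the sponsor regards any anti-fungal as distorting the outcome.* The CIP gives no reason for that criterion.
- *The two ATC groups miss vaginal products.* The documents do not reproduce the coding index, so this cannot be settled from them.

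**The remedy has its own bias.** Scoring every user as a failure will fail some women whom the pessary would have cured. This is true; it is a choice of estimand.

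**Conclusion.** The point holds as a gap in the primary definition. On its natural reading, the main analysis has no rule for an anti-fungal started for an unrelated reason between first dose and the CVVS used, and leaves the case to a review whose stated test is the reason for use. That judgement is made in an open-label trial, and no masking of the review to CVVS results is stated.

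Provided that an anti-fungal does not worsen the CVVS, the error can only raise the cure rate. Its expected size is small, because such use is probably rare, and cannot be estimated from the documents. One affected woman reverses the conclusion only when the count is exactly 11/24 or 12/26. The inflation in the illustration rests wholly on the assumed f and c. The point merits a change of wording; it does not show that the result would be wrong.

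**What to change.** **Preferred.** In SAP 7.9.2 and CIP 12.4.2, define event 1 by product and date: any systemic or vulvovaginal anti-fungal, or any other VVC treatment, started after the first dose and before the CVVS used, whatever the reason, means not clinically cured. Apply the same list in the SAP 6.2.2 review. State also whether the return to the Day 7 CVVS follows that list, so that a product started between the two visits is handled in one way.

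**Minimum.** Keep the definition and pre-specify a sensitivity analysis that scores these women as not cured.

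**Either way.** The differing statements on anti-fungals in CIP 6.4, 6.5 and 8.4 and SAP 6.2.2 must be reconciled. Which on-study restriction applies is a clinical decision for the sponsor.

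**Cost.** No new data: product and reason for use are already recorded (CIP 8.4, SAP 6.2), and SAP 7.7 already works with start and stop dates. The cure rate can only stay or fall. At n = 26 and a true 54%, scoring a share of 1/26 or 2/26 as failures lowers power from 0.841 to 0.784 or 0.716. At a true 30%, the chance of success falls from 0.060 to 0.046 or 0.034.

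Changing the primary definition needs a CIP amendment (SAP 2, CIP 13.5). SAP version 2.0 was signed on 25 March 2024, after the last-patient dates planned in the CIP, and the documents do not say whether the database was locked. If outcomes are already known, the sensitivity analysis, labelled with its date, is the safer route.

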3.3.2 Clinical data

The Gedea Pessary (*p*Hyph gen II) used in this clinical investigation has been tested in a randomised, double-blind, placebo-controlled investigation in adult women with BV, the CL3 study. The objective of the investigation was to evaluate clinical performance, and safety of initial and preventive treatment with the Gedea Pessary, as compared to placebo, in women with BV. In the part 1 of the study, treatment for 6 consecutive days was given and the clinical cure rate on Day 7, defined as absence of all of the 3 Amsel criteria was evaluated (pH excluded). 115 patients treated with *p*Hyph and 30 patients treated with placebo were included in the Full Analysis Set (FAS). There were no significant between-group differences in the percentage of women who were clinically cured; 50.4% in the *p*Hyph group and 46.7% in the placebo group. *In vitro* studies performed, showed that the placebo was not inactive, it strongly promoted the growth of *Lactobacillus Iners* and this may explain the high placebo cure rate in the CL3 study⁵⁸.

During Part 1 of the CL3 study, 26 AEs were reported by 22 patients (19.1%) in the Gedea Pessary group and 5 AEs were reported by 4 patients (13.3%) in the placebo group. The most commonly reported AEs were Vulvovaginal candidiasis (Gedea Pessary: 5 AEs in 5 patients, 4.3%; Placebo: 1 AE in 1 patient, 3.3%), Vulvovaginal burning sensation (Gedea Pessary: 3 AEs in 3 patients, 2.6%) and Vulvovaginal pruritus (Gedea Pessary: 2 AEs in 2 patients, 1.7%; Placebo: 1 AE in 1 patient, 3.3%).

A total of 8 AEs (Vulvovaginal discomfort [2 events in 2 patients], Dysmenorrhoea, Vulvovaginal pruritus, and Vaginal discharge/Vulvovaginal burning sensation/Vulvovaginal erythema/Vulvovaginal swelling [reported at the same time in 1 patient]) in 4 patients (2.8%, N=145) (Gedea Pessary: 6 AEs in 3 patients, 2.6%; Placebo: 2 AEs in 1 patient, 3.3%) were judged as possibly related. One AE (Vulvovaginal pruritus) in 1 patient (0.9%) in the Gedea

Pessary group was judged as probably related to the study procedure. Most AEs (22 AEs) were of mild intensity, except for 9 AEs (Vulvovaginal candidiasis [2 events], Back pain, COVID-19, Urinary tract infection, and Vaginal discharge/Vulvovaginal burning sensation/ Vulvovaginal erythema/Vulvovaginal swelling [reported at the same time in 1 patient]) in 6 patients (4.1%) that were assessed as moderate. No severe events were reported.

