5.4.7 Early withdrawal visit

If a patient is prematurely withdrawn from the study for any reason, the patient must be followed-up for at least safety purposes and if the patient is withdrawn prior to the Day 14 visit (if this visit is applicable), the patient should be asked to visit the site for follow-up assessments (see [Section 6.6.3](#) for withdrawal procedures).

If a withdrawal occurs during a study visit, the electronic case report form (eCRF) for that specific visit shall be completed as far as possible.

The following assessments should be performed to the extent possible on the day for early withdrawal:

- Reason for withdrawal.
- Vaginal swab (self-swab as applicable) for
 - Culture
 - Sequencing
- Recording of
 - Concomitant medications
 - Vulvovaginal signs (if a visit is performed)
 - AEs
 - Potential menstruation onset
- Product accountability – if not already performed on previous visit, patients should be asked to return all used and not used treatment packages.
- Patient questionnaire (via mobile application)
 - Vulvovaginal symptoms (itching, burning, and irritation), evaluated by patients according to a scoring scale (0-3).
 - Usability (if not already obtained).

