6.6.2 Reasons for treatment discontinuation or withdrawal from the study

Reasons for a patient to discontinue treatment or withdraw from study include, but are not limited to:

- **Informed consent withdrawal**

The patient may withdraw from the study or be withdrawn by a legal representative, if applicable, at any time without stating a reason and without prejudice to further treatment or medical care.

- **Safety reasons**

The Investigator or Sponsor may withdraw patients from treatment if judged that an AE poses an unacceptable risk or consequence to the patient.

- **Medical reasons**

The Investigator may withdraw patients from the study if judged that a medical condition poses an unacceptable risk or consequence for the patient to continue in the study. The rationale and the medical condition responsible for the Investigator-initiated withdrawal shall be documented.

- **Lost to follow-up**

Reasonable efforts shall be made to reach patients not returning for scheduled visits or not being reachable by telephone. Such efforts may include, e.g. calling the patient at least 3 times at different hours and leaving voice messages.

- **Other reasons for study withdrawal**

Other reasons include but are not limited to failure of the patient to comply with study procedures or requirements.

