6.6.3 Procedure for withdrawal of a patient

If a patient does not return for a scheduled follow-up visit, every effort should be made to contact the patient, to collect answers on the patient questionnaire and information on concomitant medications, vulvovaginal signs and AEs, if any (see [Section 5.4.7](#) for more details). If possible, the reason for withdrawal should be sought and recorded in the eCRF.

If the withdrawal from treatment is due to lack of clinical performance or for safety reasons of the investigational product, the patient will if possible continue to be followed-up in the study.

If a withdrawal from the study occurs during a study visit, the eCRF for that specific visit shall be completed as far as possible.

Any AE should be followed-up until the AE is resolved or the Investigator decides that the AE is stable and needs no further follow-up.

If a patient is not prematurely withdrawn from the study, the last day for follow-up will be Day 25 (Visit 4).

AEs ongoing at the last day for follow-up shall be assessed as chronic or stable. Wherever possible, other assessments should be carried out according to the CIP at the time of withdrawal.

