The primary endpoint clinical cure rate on Day 7-14, as defined in the section will be calculated and presented together with a one-sided 95 % CI based on the Wilson score.

The primary performance objective of the trial is to show that the clinical cure rate is above 30 %, i.e. to show that the lower limit of the one-sided 95 % CI for the observed cure rate is above 30 %.

Hypotheses for the primary clinical performance endpoint

Null hypothesis: Clinical cure rate is less than or equal to 30 %.

Alternative hypothesis (one-sided): Clinical cure rate is above 30 %.

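### Women who leave because of an adverse event, or because treatment failed after the last dose, drop out of the primary denominator if they have no Day 7-14 CVVS, which can inflate the cure rate near the 30% bound

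*SAP*

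**What the plan says.** SAP 7.9.2 and CIP 12.4.2 list the same three intercurrent events, each of which makes a patient not cured: antifungal or other VVC treatment taken for lack of performance, "Treatment discontinuation due to lack of clinical performance", and rescue medication before the CVVS that is used. Otherwise the last CVVS in the Day 7-14 interval decides, with 3 or below meaning cured. The remaining case is settled in CIP 12.4.2: "Patients with missing CVVS score at Day 7-14 and no intercurrent events will be considered as missing in the analysis". SAP 7.9.2 repeats this rule.

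SAP 7.1.5 generally imputes nothing. For sensitivity analyses of missing primary data it refers to 7.9.2, but 7.9.2 contains none. CIP 12.4.2 promises sensitivity analyses for missing CVVS items and leaves the details to the SAP.

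The CIP foresees stopping for safety. Section 6.6.2 states: "The Investigator or Sponsor may withdraw patients from treatment if judged that an AE poses an unacceptable risk or consequence to the patient". Section 6.6.3 treats the two reasons alike for follow-up: "If the withdrawal from treatment is due to lack of clinical performance or for safety reasons of the investigational product" the patient is to be followed in the study if possible. The endpoint definition makes only the first of the two a failure.

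**The concern.** Local adverse events and treatment failure can be the same observation in this disease. Itching, burning, irritation, erythema and oedema are CVVS items. CIP 3.3.2 reports burning, pruritus, erythema and swelling as adverse events with this product in CL3. Suppose two women stop on the same day with the same worsening burning and neither returns. The one recorded as lack of performance is a failure. The one recorded as an adverse event is missing. The study is open-label, so the reason is recorded by someone who knows how the patient is doing.

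The second gap does not depend on the label. Dosing ends on Day 5. A woman who takes all six pessaries and leaves before Visit 2 because they did not work has not discontinued treatment, so event 2 cannot apply to her.

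Early-withdrawal data do not close either gap. CIP 5.4.7 collects "Vulvovaginal signs (if a visit is performed") and takes symptoms by app, but SAP 7.9.2 uses only a CVVS within Day 7-14. Neither document says whether a score from a withdrawal visit inside that interval counts.

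With no control arm, a bias in the observed rate carries straight into the comparison with 30%.

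**Working it through.** **Inputs.** The result is "presented together with a one-sided 95 % CI based on the Wilson score" (SAP 7.9.2), so z = 1.645. The null is "Null hypothesis: Clinical cure rate is less than or equal to 30" per cent (SAP 7.9.2). The assumed rate is 54%, with 24 evaluable and 26 enrolled to allow for missing data (SAP 5.1, CIP 12.6). The number of women lost before any Day 7-14 CVVS is not given, so it is varied below as an assumption.

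**The plan's own figure.** n = [(1.645 × √(0.30 × 0.70) + 0.842 × √(0.54 × 0.46)) / 0.24]² = [(0.754 + 0.419) / 0.24]² = 23.9, so 24. The stated sample size reproduces.

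**Lower limit.** L = [p + z²/(2n) − z√(p(1−p)/n + z²/(4n²))] / (1 + z²/n). For 11/24: (0.4583 + 0.0564 − 0.1765) / 1.1127 = 0.304.

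With 26 dosed and 11 cured:

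| Women with no Day 7-14 CVVS | Dropped as missing (plan) | All counted as not cured |
|---|---|---|
| 0 | 11/26, 27.8%, fails | 11/26, 27.8%, fails |
| 1 | 11/25, 29.1%, fails | 11/26, 27.8%, fails |
| 2 | 11/24, 30.4%, succeeds | 11/26, 27.8%, fails |
| 3 | 11/23, 31.8%, succeeds | 11/26, 27.8%, fails |

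Success needs 11 cures at n = 24 (10/24 gives 26.8%) and 12 at both n = 25 (32.6%) and n = 26 (31.2%). So if only one patient is missing, her handling never matters. If two are missing, it matters only at 11 cures, and counting just one of them as not cured (11/25) is enough to reverse the result. Two is the total allowance in the plan (26 − 24), for missing data of any kind. Three or four missing also matter only at 11 cures; five matter at 10 or 11.

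**Away from the boundary.** With 14 cured and two missing the decision stands, but the estimate is 14/24 = 58.3% instead of 14/26 = 53.8%.

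**Long-run illustration (assumed, worst case).** Suppose the true rate in all 26 is 30%, only failures are lost, and each failure has probability d of being lost. The rate being estimated becomes 0.30 / (0.30 + 0.70(1−d)), and 26 × 0.70 × d women are missing on average. Exact enumeration of the Wilson rule gives the chance of success:

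| d | Expected missing | Rate estimated | Chance of success |
|---|---|---|---|
| 0 | 0 | 30.0% | 6.0% |
| 5% | 0.9 | 31.1% | 7.2% |
| 10% | 1.8 | 32.3% | 9.1% |
| 20% | 3.6 | 34.9% | 14.1% |

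**The case against.** Stopping for an adverse event does not in itself make a woman missing. CIP 6.6.4 keeps patients who discontinue treatment in the study, and 5.4.7 asks those withdrawing before an applicable Day 14 visit to attend. Any Day 7-14 CVVS then decides, and a score above 3 is a failure whatever the reason for stopping. A woman who leaves after Visit 2 has her Day 7 score used. A failing woman who takes another VVC treatment before the CVVS can fall under event 1, and SAP 6.2.2 has concomitant medication reviewed before lock for this purpose. All of this stands, and it confines the problem to women with no Day 7-14 CVVS and no such treatment.

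A reader might infer that sites will default to the adverse-event or consent label because 6.6.2 has no heading for lack of performance. The documents do not support that: the list is expressly open-ended, and 6.6.3 names lack of performance as a reason.

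The numbers may be small. Burning was reported as an adverse event in 3 of 115 CL3 patients (2.6%), about 0.7 of 26, and not all would stop and be lost. The one adverse-event exit described for CL1 followed a rash judged unrelated to the product. At the planned 54%, exactly 11 cures among 26 has probability C(26,11) × 0.54¹¹ × 0.46¹⁵ = 7.7%. This limits the size of the concern but does not remove the gap.

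It is also tempting to fail any woman whose last score before Day 7 is above 3. Inclusion requires at least two items at moderate or worse, hence a baseline CVVS of at least 4, so that rule would fail women whose baseline had not yet had time to resolve.

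**Conclusion.** The gap is real but conditional. The intercurrent-event list omits adverse-event discontinuation or withdrawal, and withdrawal for lack of performance after dosing, and such women with no Day 7-14 CVVS leave the denominator. A reader might infer that every woman who stops for an adverse event is lost, or that the cure rate is inflated. The documents support only that it can be, if women lost in this way are more often failures than those observed. That is plausible but not shown.

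With two or more missing, the effect can decide the trial at 11 cures; otherwise it shifts the estimate by a few percentage points. The long-run figures rest on the assumption that only failures are lost, so they are upper bounds. Because the sensitivity analysis is absent from SAP 7.9.2, a reader of the results could not tell whether the conclusion depends on the dropped patients. This is a cheap improvement, not a flaw that undermines the design.

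**What to change.** In SAP 7.9.2 and CIP 12.4.2, keep event 2 and add: *Permanent treatment discontinuation due to an adverse event, or study withdrawal due to lack of clinical performance or an adverse event, with no Day 7-14 CVVS available: not clinically cured.* State that where a Day 7-14 CVVS exists after an adverse-event discontinuation, that score decides. Overriding an observed score would be a different estimand, not a correction.

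In SAP 7.9.2, specify the sensitivity analysis to which 7.1.5 refers: every FAS patient without a Day 7-14 CVVS is counted as not cured, the denominator is the whole FAS, and the same one-sided 95% Wilson limit is used. This also covers consent withdrawal and loss to follow-up, which stay missing in the main analysis, so it shows how much rests on the recorded reason.

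No new assessment, visit procedure or eCRF item is needed. That matters because the last visit was planned for Q4 2023 at the latest (CIP 13.7) and the SAP was signed on 25 March 2024. The cost is a few lines in two documents, one extra table row, and a cure rate that may be slightly lower. The wording should be fixed before database lock; if that has passed, the sensitivity analysis can still be reported and labelled as added afterwards.
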